2.2 BACKGROUND

In a prior study,² we asked people on a 10-point scale how likely they were to have had COVID-19. About 20% of the sample reported 7 or higher on this 10-point scale, however only 4% of the sample tested positive. This suggests antibody testing has a large potential to correct beliefs about past infection and promote retesting for those who are antibody negative. However, a positive test could potentially reduce willingness to participate in repeat testing. Among those who tested positive, about 23% of the sample reported a 1 or 2 on a 10-point scale on how likely they were to have had COVID-19. These people may be less likely to retest for studies trying to depict the immune response over time. Underserved populations face different barriers to testing and these may vary within different communities and households. The diversity in Los Angeles allows us to assess how barriers to antibody testing differ for vulnerable groups. Data from our prior study show that Blacks and Latinos were 27 percentage points and 14 percentage points less likely to participate in testing compared to their white counterparts.² We also find that those with household income less than \$50,000 were 17 percentage points less likely to take-up antibody testing compared to those with household income greater than \$100,000. It is important to understand why these disparities exist. The proposed research will shed light on this issue by evaluating barriers/facilitators of testing including

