9.2 SAMPLE SIZE DETERMINATION

We will recruit a cohort of 2,160 people (540 families), and stratify into 3 subgroups based on predictors of commitment to participation in testing programs. Randomization will be clustered by family. Sub-group membership will be based on the mean household survey response to the survey component. For the purposes of power analyses, we assume high Intra Cluster Correlation within family on uptake of repeat testing (>0.90).

Stratified Allocation Plan and Power Analysis (540 households, 2160 individuals)		
	Control	Intervention
Stratification	# households	# households
HTE Subgroup 1	60	60
HTE Subgroup 2	60	60

HTE Subgroup 3	60	60
% Seropositive in Baseline Test	10%	10%
Total Households Per Arm	180	180
Projected Average Treatment Effect Size	Reference Group	Reference+10%
Minimum Detectable Effect Size Compared to Controls (H4r)	±3%	
Detectable 3-subgroup HTE and Seropositivity (H1r, H2r, H3r)	±7%	

Assuming a similar effect size to prior studies in similar populations, we expect a 10 percentage point difference in repeat testing adherence between intervention and control groups. With 540 households, we are powered to detect as little as 3 percentage point difference between interventions and controls in the 540 households we will enroll. To assess heterogeneity of treatment effects (THE), there is more than 80% power to detect a between-subgroup difference of 7 percentage points, assuming 180 households in each sub-group.

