9.4 STATISTICAL ANALYSES

9.4.1 GENERAL APPROACH

Aim 1 (Hypotheses 1-5): Data from the baseline survey combined with data on which heads of households attended Time 1 testing will be used to address Aim 1. In particular, we will estimate logistic regressions where the dependent variable will be the binary indicator whether the head of household attended Time 1 testing (yes vs. no). The key independent variables will include: 1) prior COVID-19 testing, 2) which SARS-CoV-2 information sources are most trusted, 3) risk aversion, 4) heads of households or family member diagnosis of a health condition (e.g., diabetes, hypertension) and, 5) race/ethnicity, income, discriminatory incidences, household receipt of Supplemental Nutrition Assistance Program (SNAP) or Supplemental Security Income (SSI) benefits, and citing money as the biggest vaccine barrier.

$$\pi = \beta_0 + \beta_1 x_i + \varepsilon_i \quad [1]$$

$\pi = \ln\left(\frac{p}{1-p_i}\right)$; p_i , is the probability of attending Time 1 testing, by head of household i , and β_1 is each head of household reported social determinant of health. This will allow us to identify significant social and behavioral determinants for heterogeneity of effects (currently hypothesized in Hypotheses 1-5 above).

Aim 2 (Hypotheses 1r-4r): Aim 2 will involve regressing Time 2 retesting (yes vs. no) on the following items for Hypotheses 1r-4r: 1r) risk aversion, essential worker status, access to personal protective equipment, and risky forms of transportation (e.g., personal vehicle, carpool, bus), 2r) income, discriminatory incidences, employment status, whether heads of households personally, or other family members suffer from depression and/or mental health issues, and household receipt of Supplemental Nutrition Assistance Program (SNAP) or Supplemental Security Income (SSI) benefits, 3r) Time 1 seropositivity status and, 4r) the Financial Incentive and Messaging study arms.

$$\pi = \beta_0 + \beta_1 x_i + \beta_2 x_i + \beta_3 x_i + \varepsilon_i \quad [2]$$

For Hypotheses 1r-2r, $\pi = \ln\left(\frac{p}{1-p_i}\right)$, is the probability of Time 2 attendance by head of household i given they attended Time 1 testing; β_1 is the main effect of the head of household reported characteristic, β_2 is the main effect of the Financial Incentive, where the lottery condition is the reference, and β_3 is the interaction between the head of household reported social determinant of health and Financial Incentive.

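### Section 9.2 sizes heterogeneity (H1r, H2r) in percentage points, but Model 2 tests it only as a log-odds interaction and no percentage-point contrast is planned for it

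*Combined protocol and SAP*

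**What the plan says.** Section 9.2 puts its design quantities in percentage points. For the average effect, "we expect a 10 percentage point difference in repeat testing adherence between intervention and control groups". For heterogeneity, "there is more than 80% power to detect a between-subgroup difference of 7 percentage points, assuming 180 households in each sub-group". The last row of its table attaches the 7-point figure to H1r, H2r and H3r.

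Section 9.1 classes H1r and H2r as heterogeneity of treatment effects on retesting; H2r concerns which people respond most to insurance. Section 9.4.1 tests both with Model 2, a logistic regression of Time 2 attendance among heads of household who attended Time 1. The heterogeneity term is β3, which "is the interaction between the head of household reported social determinant of health and Financial Incentive".

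For Models 4a and 4b (H4r), Section 9.4.1 adds bootstrap confidence intervals for probability differences. It does not do so for Model 2. Section 9.4.2 reuses Model 2 to compare response to study arm across social determinants, and names no scale.

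**The concern.** A difference in percentage points and a ratio of odds ratios are different measures of heterogeneity. When subgroups start from different retest rates, one can be zero while the other is not, and they can rank the subgroups in opposite order.

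The plan wants to learn which groups each facilitator suits best, so the ranking is the product. A programme planner who reads β3 would favour the group with the larger odds ratio. That need not be the group in which more additional people come back. In addition, the 7-point figure in Section 9.2 is not a property of the test that will be run.

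**Working it through.** **Inputs from the documents.** Average effect 10 points; heterogeneity target 7 points; 540 households; 180 households per subgroup (Section 9.2). Model 2 on the logit scale, restricted to heads who attended Time 1 (Section 9.4.1).

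**Assumptions.** The documents give no retest rate, and Section 9.2 gives no alpha. I use two-sided 0.05 and a range of rates. A binary moderator splitting 540 heads evenly gives 540/4 = 135 per moderator-by-incentive cell. Two subgroups of 180 give 90 per cell. Both are upper bounds, because heads who miss Time 1 drop out of Model 2.

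**1. The plan's own figure.** Power above 80% at 7 points cannot be confirmed without a control rate.
- Read as 180 v 180 households compared on retest rate, power is 83% at 2% v 9%, 26% at 50% v 57% and 90% at 92% v 99%.
- Read as a difference in effects (6.5 v 13.5 points, 90 per cell, 50% control rate in both subgroups), SE = √[(0.250 + 0.246 + 0.250 + 0.232)/90] = 0.104. Power = Φ(0.07/0.104 − 1.96) = 10%. Over control rates from 1% to 86% it runs from 10% to 30%.

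Neither reading is a calculation for β3.

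**2. Formulas for the scale comparison**, for subgroups A and B:
- Point contrast = (pB1 − pB0) − (pA1 − pA0)
- β3 = ln(OR_B) − ln(OR_A), where OR = [p1/(1 − p1)] / [p0/(1 − p0)]
- Var(β3) = Σ 1/[n p(1 − p)] over the four cells

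**3. Equal 10-point gains (point contrast zero).** Wald rejection rates at n = 135:

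| A | B | OR_A | OR_B | Ratio | Rejection |
|---|---|---|---|---|---|
| 40→50% | 57→67% | 1.50 | 1.53 | 1.02 | 5.0% |
| 50→60% | 67→77% | 1.50 | 1.65 | 1.10 | 5.8% |
| 60→70% | 77→87% | 1.56 | 2.00 | 1.29 | 9.2% |
| 50→60% | 80→90% | 1.50 | 2.25 | 1.50 | 15.4% |

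For the last row, Var = (4 + 4.167 + 6.25 + 11.111)/135 = 0.189, SE = 0.435 and β3 = 0.405. Simulation gives 14.0% for that row, and 10.3% at 90 per cell.

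**4. Reversal at the plan's own 7-point margin.** A: 50→67%, +17 points, OR = (0.67/0.33)/1 = 2.03. B: 80→90%, +10 points, OR = 9/4 = 2.25. The point contrast is −7; β3 = ln(2.25/2.03) = +0.103. In 200,000 simulated trials the two estimated interactions had opposite signs in 34% at 90 per cell and 41% at 135. With B at 85→95%, β3 = +0.502 and the figures are 56% and 67%.

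**5. The converse.** A common odds ratio of 1.5 makes β3 zero. Yet 50→60% is +10 points, while 80→85.7% (odds 4 × 1.5 = 6, and 6/7 = 0.857) is +5.7.

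**The case against.** A logistic interaction is standard, and quoting detectable effects in points before a logistic analysis is common. Section 9.2 is a power section and does not formally fix an estimand. Its 7-point row also covers H3r, which Section 9.1 calls a main effect, so the figure may mean a difference in rates. H2r names no scale. A β3 away from zero under equal point gains is a false signal only if the point scale is the chosen one. All of this stands. A reader might infer that Model 2 is the wrong model; the documents do not support that.

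A reader might also infer from Section 2.2, where "Blacks and Latinos were 27 percentage points and 14 percentage points less likely to participate in testing", that the subgroups here start far apart and that false signals will be frequent. With a 27-point gap and equal 10-point gains, 55→65% v 82→92% gives 20% rejection and 60→70% v 87→97% gives 45% (Wald, 135 per cell). That inference fails for three reasons.
- Those gaps are first-test uptake in a prior study by race and ethnicity. Model 2 concerns return among heads already tested, and race and ethnicity are not among the H1r or H2r moderators.
- The Section 2.2 gap that does match a listed moderator is income, at 17 points, and it too is uptake. The first three rows of the table use a 17-point gap and give 5% to 9%.
- 135 per cell supposes that every head attends Time 1. With about half attending (assumed, 68 per cell), simulation brings the 20% and 45% down to roughly 9% to 13%.

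What the objection does not remove is that the plan states its target in points, gives point-scale results for H4r, and gives none for H1r and H2r.

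**Conclusion.** The concern holds as a mismatch between the sizing scale and the testing scale, with no planned bridge between them. Following the plan, the 7-point quantity for H1r and H2r is never estimated.

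The consequence is conditional. With mid-range retest rates in both subgroups the scales give practically the same answer. With one subgroup near 80% to 90% they can rank groups differently, including at a true 7-point difference. The false-signal side is modest in the cases that do not rest on a near-ceiling cell. The ranking side matters more, because ranking is what H2r asks about and it does not fade with a larger sample. The size in this trial is unknown, since every rate used above is assumed. This calls for a correction to the analysis text; it does not undermine the design.

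**What to change.** For H1r and H2r, add to Section 9.4.1 that Model 2 will also yield the difference between subgroups in the insurance-minus-lottery predicted retest probability, in percentage points, as the measure that matches Section 9.2. Report it alongside β3. For the reuse of Model 2 in Section 9.4.2, report the corresponding arm contrast on the same scale.

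- **Interval:** bootstrap by resampling heads of household, with the resample size equal to the number of heads analysed. Do not carry over the 3,000-observation draw set for Models 4a and 4b. Model 2 has at most 540 heads, so that draw would narrow intervals by a factor of about √(3000/540) = 2.4.
- **Continuous moderators:** evaluate the contrast at values fixed in advance.
- **Section 9.2:** state that the 7-point figure does not describe the β3 test.

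The cost is SAP wording and a little more analysis, with no new data or participants. The point-scale interval may be wide, and the report should say so.

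### The stated heterogeneity power is for a three-subgroup test that no model runs; H1r and H2r are instead tested by about nine item-level interactions with no multiplicity control and no power of their own

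*Combined protocol and SAP*

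**What the plan says.** Section 9.2 plans to "stratify into 3 subgroups based on predictors of commitment to participation in testing programs". On how a household is placed it says only this: "Sub-group membership will be based on the mean household survey response to the survey component". The allocation table has rows for HTE Subgroups 1 to 3 and gives ±7% against the row "Detectable 3-subgroup HTE and Seropositivity (H1r, H2r, H3r". The text below it says that "there is more than 80% power to detect a between-subgroup difference of 7 percentage points, assuming 180 households in each sub-group".

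Section 9.4.1 tests H1r and H2r with Model 2, a logistic regression of Time 2 attendance among heads of household who attended Time 1. It contains one reported characteristic, the financial incentive and their product; the last coefficient "is the interaction between the head of household reported social determinant of health and Financial Incentive". The items listed are:

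- H1r (4): risk aversion, essential-worker status, access to protective equipment, and transport.
- H2r (5): income, discrimination, employment, depression or mental health problems in the head or family, and SNAP/SSI receipt.

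Section 9.4.2 reuses Model 2 for determinants found significant under Hypotheses 1-5. Section 9.4.6 mentions sex/gender and race/ethnicity only. No alpha, hierarchy or adjustment is stated for any of these tests.

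**The concern.** A power statement supports a trial only if it describes an analysis that will be done. Here the one heterogeneity test with a power figure has no model, and the tests that will be done have no power figure. A reader of Section 9.2 would take H1r and H2r to be well powered.

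These are numbered hypotheses. Section 9.1 says that they concern heterogeneity of treatment effects, and Section 3 lists interactions with covariates in its primary row. Two errors are therefore possible: a chance interaction among several items could be reported as support for tailoring incentives, or a null result could be read as evidence of no heterogeneity when the test had little chance of finding any.

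**Working it through.** **1. Does any model use the subgroup?**

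- Model 1: head-of-household determinants of Time 1 attendance.
- Model 2: one head-of-household item, incentive, and their product.
- Model 3: Time 1 seropositivity.
- Model 4a: time, incentive, messaging, and time by each factor.
- Model 4b: time, arm, and time by arm.
- Sections 9.4.2 and 9.4.6: Model 2 again, and sex/gender and race/ethnicity.

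None has a three-level subgroup term. Model 2 is not the same test under another name: its covariate is a single item, whereas the subgroup rests on a household score.

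**2. The plan's 7-point figure.** Section 9.2 gives 540 households, 2,160 people (4 per household), 180 households per subgroup and an intra-cluster correlation above 0.90. It does not give alpha or the reference retest rate, so the figure cannot be reproduced uniquely. I assume two-sided 5% and compare two subgroups directly:

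- 180 households each: power for 7 points is 26-49% at reference rates of 10-80%.
- Clustered people: design effect 1 + 3 × 0.9 = 3.7, so 720/3.7 ≈ 195 effective per subgroup; power is 28-52% over the same rates.
- 720 people each with clustering ignored: 80.4% at a 30% reference rate, with a detectable difference of 7.0 points.

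The last line matches the stated figure, but the documents do not show that it was obtained that way.

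**3. Power of the Model 2 test.** Assumptions: all 540 heads attend Time 1, a 50:50 binary item, equal incentive arms (so 540/4 = 135 per cell), and a common retest rate p. On the probability scale:

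SE = √(4p(1−p)/135); power = Φ(0.07/SE − 1.96) + Φ(−0.07/SE − 1.96).

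| p | SE | Power for 7 points | Detectable at 80% (2.80 × SE) |
|---|---|---|---|
| 0.2 | 0.069 | 17% | 19 points |
| 0.5 | 0.086 | 13% | 24 points |
| 0.7 | 0.079 | 14% | 22 points |

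Non-attendance at Time 1 or an unbalanced item lowers these figures.

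**4. Power of an incentive-by-subgroup contrast.** Two subgroups of 180 households, each split by incentive, give 90 per cell. The same formula with 90 gives SE 0.084 and power 13% at p = 0.2, SE 0.105 and power 10% at p = 0.5, and SE 0.097 and power 11% at p = 0.7. The table's own layout (60 + 60 = 120 households per subgroup) would give less.

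**5. False positives over the items** (5% per test assumed, all nulls true).

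- Nine independent tests: 1 − 0.95⁹ = 37%; expected number 9 × 0.05 = 0.45.
- Nine tests with equally correlated statistics, by simulation: 32.7% at 0.3, 26.9% at 0.5, 20.3% at 0.7.
- H1r alone, if independent: 1 − 0.95⁴ = 19%. H2r alone: 1 − 0.95⁵ = 23%.

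Fitting the items jointly would still give one test per item.

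**The case against.** The best defence is that Model 2 is the right test of H1r and H2r. Section 9.1 links particular traits (risk-seeking and exposure; low income, unemployment and stress) to response to a particular incentive, and Model 2 follows that mapping. The Section 9.2 subgroups rest on predictors of commitment to testing, which is a different construct. Carrying determinants of attendance from Model 1 into Model 2 also covers part of that construct, and Section 9.4.2 describes its own heterogeneity work as exploration. This much stands: Model 2 should not be displaced. It does not supply the missing subgroup test, and the exploratory wording is in Section 9.4.2, not in the Section 9.4.1 tests of H1r and H2r.

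A reader might infer three stronger points that the documents do not support:

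- *That a 37% false-positive risk would fall to 5% with one subgroup test.* The 37% assumes independence and pools two separate hypotheses. Section 9.2 does not specify a single 2-df test, and one such test for each of two factors would give 1 − 0.95² = 9.8%.
- *That a subgroup test would recover power.* Step 4 shows that it does not: any two subgroups compare 180 with 180 households, a balanced item 270 with 270.
- *That the subgroup variable is ready to use.* Section 9.2 gives no items, score or cut-points. Section 5.5 has one adult per household answering the survey, so a household mean is unclear. Section 9.4.5 sets stratification thresholds after a week of testing, and the randomization steps in Section 6.3 do not mention the three strata.

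**Conclusion.** The concern holds as a mismatch between Sections 9.2 and 9.4. The absence of the subgroup from every planned model is plain from the text and needs no assumption. The figures do need assumptions: two-sided 5% per test, a count of nine items, full Time 1 attendance, balanced binary items and retest rates of 20-70%. On these, item-level power for a 7-point interaction is about 13-17%, far below the stated 80%. The chance of at least one false positive is about 20-37% over the nine items, depending on their correlation, or 19% and 23% by hypothesis if independent. The H4r comparison of incentives and messaging is not affected. The plan should be changed, but this does not call the main trial result into question.

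**What to change.** 1. In Section 9.4.1, state the subgroup scoring and cut-points before outcome data are seen. Add the three-level subgroup and its interaction with incentive to the Time 2 model, and name the 2-df interaction test as the heterogeneity test that Section 9.2 describes. Label any messaging-by-subgroup test exploratory, since neither H1r nor H2r concerns messaging.
2. Keep the Model 2 item interactions as the tests of H1r and H2r, with a multiplicity adjustment within each hypothesis. Holm, for example, starts at 0.05/4 = 0.0125 for H1r and 0.05/5 = 0.01 for H2r.
3. In Section 9.2, replace the 7-point, 80% statement with the power or detectable difference recomputed for these interaction tests, giving alpha, the assumed retest rate and the unit of analysis.

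The cost is one extra model, a written scoring rule, somewhat stricter per-item thresholds and a less favourable power statement. No new data are needed.

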beliefs about COVID-19, mistrust of healthcare, insurance, and cultural factors. More importantly, we will study the behavioral, social and cultural factors that make actionable facilitators minimally and maximally effective. Many individuals may react differently to antibody test results. Our preliminary analysis suggests that the reactions to test results vary across subgroups. For example, lower income families and minorities are more likely to test positive, but less likely to think they have already had COVID-19. This mismatch between beliefs and serostatus might imply lower motivation to receive testing. Similarly, a larger portion of Blacks and Latinos are low-income, and many cannot work from home. A positive antibody test could have a larger increase in economic activity for this population if their perceived risk of leaving the house for work is reduced. This study will allow for improved understanding of the factors contributing to uptake of COVID-19 testing in underserved populations, and enhance our understanding of public health and health behaviors.²

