9.1 STATISTICAL HYPOTHESES

The figure below provides a conceptual diagram for thinking about what factors may influence testing take-up and retesting. Testing take-up would depend on several factors, including prior beliefs about infection, health literacy, information networks, health conditions, demographics and socio-economics. We have the following hypothesis based on analysis of literature on testing for HIV and Hepatitis as well as preliminary analysis of data from our prior study:

Hypothesis 1: Those who believe that they have been infected in the past would be more likely agree to testing to confirm that they have antibodies and potential immunity; **Hypothesis 2:** People with poor health literacy will be less likely to agree to testing as they might find it daunting to understand what the test does and how to interpret results; **Hypothesis 3:** Those who are risk averse would be more likely to agree to testing as it reduces uncertainty about serostatus; **Hypothesis 4:** Those with preexisting health conditions would be more likely to agree to testing as they face higher risks from COVID-19 and thus have more to gain from learning serostatus; **Hypothesis 5:** Minorities and those in lower socio-

economic strata would be less likely to agree to testing due to fear of discrimination, lack of trust in health care/research, poor past experience, and perception of being at low risk of infection. We also generate hypotheses for facilitators to retesting (r) relative to those who take a first test **Hypothesis 1r:** Persons who practice low COVID-19 mitigation, exhibit risk-seeking and have high exposure risk may respond to a lottery retest incentive. **Hypothesis 2r:** Those persons with low income, unemployed, or have high stress or anxiety may respond most to insurance of incentives. **Hypothesis 3r:** Persons who are sero+ at baseline will be less likely to return for a retest. **Hypothesis 4r:** Lottery insurance and family messaging will induce higher retesting rates. Hypotheses 1-5 are covariates that may affect agreeing to the test. Hypotheses 1r and 2r refer to heterogeneity of treatment effects for retesting, while 3r and 4r are main effects on retesting.

Conceptual diagram

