$$\pi = \beta_0 + \beta_1 x_{ij} + \eta_j + \varepsilon_i \quad [3]$$

For Hypothesis 3r, we will use a simple mixed-effects logistic model, where $\pi = \ln\left(\frac{p}{1-p_i}\right)$, is the probability of Time 2 attendance by individual i in household j given they attended Time 1 testing; β_1 is seropositivity status at Time 1 (yes vs. no); and η_j is the random intercept for each household capturing household-level effects.

We will use two separate models for Hypothesis 4r.

$$\pi = \beta_0 + \beta_1 x_{ij} + \beta_2 x_{ij} + \beta_3 x_{ij} + \beta_4 x_{ij} + \beta_5 x_{ij} + \eta_j + \varepsilon_i \quad [4a]$$

Model 4a will assess the probability, $\pi = \ln\left(\frac{p}{1-p_i}\right)$, of testing attendance for individual i in household j , where β_1 is the main effect for testing time (reference = Time 1); β_2 is the main effect for Financial Incentives (reference = lottery condition); β_3 is the main effect for Messaging (reference = personal); β_4 is the interaction between testing time and Financial Incentives; β_5 is the interaction between testing time and Messaging; and η_j is the random intercept for each household.

$$\pi = \beta_0 + \beta_1 x_{ij} + \beta_2 x_{ij} + \beta_3 x_{ij} + \beta_4 x_{ij} + \beta_5 x_{ij} + \beta_6 x_{ij} + \beta_7 x_{ij} + \eta_j + \varepsilon_i \quad [4b]$$

Model 4b will assess the probability, $\pi = \ln\left(\frac{p}{1-p_i}\right)$, of testing attendance for individual i in household j , where β_1 is the main effect for testing time (reference = Time 1); β_2 through β_4 are the main effects for study arm (personal messaging and loss protection, family messaging and lottery, family messaging and loss protection), where personal messaging and lottery is the reference group; β_5 through β_7 are the interactions between study arm and testing time; and η_j is the random intercept for each household.

For Models 4a and 4b, we will use unrestricted random sampling to select 3,000 observations, 2,000 times, clustered by household to bootstrap 95% confidence intervals for probability differences. We

will test differences in effect sizes for Model 4a (β_4 vs. β_5) and 4b (β_5 vs. β_6 ; β_5 vs. β_7 ; β_6 vs. β_7) using equality of regression coefficients tests.⁶ We will also calculate the inverse of observed probabilities to derive the Number Needed to Intervene on (NNI), and calculate standard errors by taking the square root of $P * (1 - P)/N$.⁷

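### Model 3 compares retesting by non-randomised serostatus with no fixed covariates, so its odds ratio can be modestly biased in the direction H3r predicts

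*Combined protocol and SAP*

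**What the plan says.** Section 9.1 states H3r as a directional claim: "Persons who are sero+ at baseline will be less likely to return for a retest". It then groups H3r with the hypothesis on the randomised arms: "while 3r and 4r are main effects on retesting".

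In Section 9.4.1 the Aim 2 item list gives serostatus alone for this hypothesis: "3r) Time 1 seropositivity status and, 4r) the Financial Incentive and Messaging study arms". Model 3 follows that list: "For Hypothesis 3r, we will use a simple mixed-effects logistic model". It is fitted to people who attended Time 1 testing and has one fixed coefficient, for Time 1 serostatus. Its only other structural term "is the random intercept for each household capturing household-level effects". Neither Section 9.4.1 nor the secondary and subgroup sections give an adjusted or sensitivity version for H3r.

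Section 2.2 describes the groups concerned. On serostatus: "lower income families and minorities are more likely to test positive, but less likely to think they have already had COVID-19". On participation: "Blacks and Latinos were 27 percentage points and 14 percentage points less likely to participate in testing compared to their white counterparts". It also reports 17 points lower uptake for household income under $50,000 than for income over $100,000.

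**The concern.** People who test positive differ from those who test negative before anyone learns a result. The plan's own background names characteristics linked both to being positive and to taking part less. Both links push the serostatus coefficient in the same direction, towards fewer positives returning, which is what H3r predicts.

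This matters because the plan invites an effect reading. Section 2.1 speaks of the effect of learning one's first result, Section 2.2 suggests that a positive result may lower willingness to retest, and Section 9.1 labels H3r a main effect. A negative coefficient from Model 3 could then be taken as a response to the result when part of it reflects who tends to be positive.

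The household intercept does not settle this. A random intercept is assumed independent of the predictors. If poorer households are both more often positive and less likely to return, that assumption fails. The intercept moves weight towards within-household comparison, which helps, but it is not adjustment for income or ethnicity.

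**Working it through.** **1. The plan's own figure.** The table in Section 9.2 gives ±7 points as detectable for seropositivity. It states neither alpha nor the reference retest rate, so I assume two-sided 5% and 80% power. Positives: 10% of 2,160 = 216; negatives: 1,944. Families average 2,160/540 = 4 people, so at ICC 0.90 the design effect is 1 + 3 × 0.90 = 3.7.

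Detectable difference = (1.960 + 0.842) × √[p(1−p) × (1/216 + 1/1,944) × 3.7]

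- At p = 50%: 19.3 points. At p = 10% or 90%: 11.6 points. About 7 points is reached only at a rate of roughly 3–4% (or 96–97%).
- With ICC 0 (no design effect): 6.0 points (p = 10%) to 10.0 points (p = 50%).
- Using within-household variance p(1−p)(1−0.90): 1.9 to 3.2 points over the same rates.

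The ±7 can be neither confirmed nor refuted from the documents. The point below does not depend on it.

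**2. Spurious crude difference with no serostatus effect.**

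Difference = −gap × [P(group | positive) − P(group | negative)]

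From the documents: 10% positive overall (9.2) and gaps of 14, 17 and 27 points (2.2). Assumed: the lower-uptake group is 50% to 90% of the sample, it is positive 1.5 to 3 times as often as the rest, and the gaps apply to retesting.

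Example with share 50% and ratio 2. Positivity is 13.3% v 6.7%. P(group | positive) = 0.5 × 0.133/0.10 = 0.667. P(group | negative) = 0.5 × 0.867/0.90 = 0.481. The difference is 0.185, which gives:

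| Share, ratio 2 | Gap 14 | Gap 17 | Gap 27 |
|---|---|---|---|
| 50% | −2.6 | −3.1 | −5.0 |
| 80% | −1.4 | −1.7 | −2.7 |
| 90% | −0.7 | −0.9 | −1.4 |

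Over the whole grid the range is −0.5 (share 90%, ratio 1.5, gap 14) to −7.5 (share 50%, ratio 3, gap 27).

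**3. Model 3 as written, with no true effect.** Simulation of 540 households of 4: random-intercept logistic regression by maximum likelihood, two-sided 5% likelihood-ratio test, 600 runs per scenario. The retest rate in the lower-uptake group (50%) and the household correlation of serostatus are assumed. The last two columns add the confounding group as a covariate. "Sig." is the share of runs significant in the H3r direction; nominal is 2.5%, with Monte Carlo standard error √(0.025 × 0.975/600) = 0.6 points.

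| Share, ratio, gap | Retest ICC | Serostatus ICC | Median OR | Sig. | Adjusted OR | Adjusted sig. |
|---|---|---|---|---|---|---|
| 50%, 2, 27 | 0.9 | 0.3 | 0.86 | 2.8% | 0.99 | 1.3% |
| 80%, 2, 17 | 0.9 | 0.3 | 0.92 | 2.3% | 0.96 | 1.7% |
| 50%, 2, 27 | 0.5 | 0.3 | 0.86 | 8.5% | 0.98 | 2.8% |
| 50%, 2, 27 | 0.2 | 0.3 | 0.85 | 12.3% | 1.00 | 2.2% |
| 50%, 3, 27 | 0.5 | 0.7 | 0.69 | 15.7% | 0.98 | 2.2% |

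The odds ratio is below 1 in every scenario and returns to 0.96–1.00 after adjustment. At ICC 0.9 the significance rate cannot be told apart from nominal.

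**4. Differences within a family.** Section 5.5 requires at least one adult and one child per household, so age varies within families by design. The documents give neither serostatus nor retesting by age, so no figure can be put on this. If the ICC of 0.90 is on the observed scale, two members of a family differ in returning with probability 2p(1−p)(1−0.90), or 5.0% at p = 50%. That leaves little room for an age difference in retesting.

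**The case against.** There are four serious arguments on the other side.

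- **The uptake gaps are not retest gaps.** They come from first-test uptake in a prior study, and the 17-point figure compares two distant income bands. Model 3 covers only people who have already accepted one test. This stands: carrying the gaps over is an assumption, and the size depends on it.
- **The confounder has little spread here.** Section 9.3 describes the clinic population as overwhelmingly low-income and minority. This stands: at a 90% share and ratio 2, the crude bias is 0.7 to 1.4 points.
- **At the plan's ICC the test is barely affected.** This also stands. A reader might infer that confounding alone could readily produce a significant H3r result under the plan's assumptions. It does not: the rate is 2.3% to 2.8% against 2.5%. What remains is a shift in the estimate. The ICC above 0.90 is, however, a power assumption and not an estimate.
- **H3r as worded is an association, which an unadjusted model can describe.** This is true, and Section 2.2 has a descriptive interest in who is lost to follow-up of the immune response. It does not cover the effect reading that Sections 2.1, 2.2 and 9.1 invite.

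A reader might also infer that adult–child differences within families bias Model 3 towards H3r. The documents do not support a direction: if adults were more often positive and also returned more often than children, the bias would run against H3r.

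**Conclusion.** Model 3 gives an unadjusted association for an exposure that is not randomised, and the household intercept controls confounding only in part. If the uptake gaps in Section 2.2 extend to retesting, the odds ratio is biased below 1, in H3r's favour. The size is modest: a crude gap of about 0.5 to 7.5 points, towards the lower end where nearly everyone is low-income, and a Model 3 odds ratio of about 0.86 to 0.92 at ICC 0.9 with no true effect. Inflation of false positives is negligible at that ICC and becomes material only if the real ICC is lower (8.5% at 0.5, 12.3% at 0.2). The positivity ratio, group share, serostatus correlation, reference retest rate and transfer of the gaps are all assumed. Confounding by age within families is possible, but of unknown direction and size. The change is worth making because the estimate would otherwise be hard to interpret as an effect, not because the test is shown to fail under the plan's assumptions.

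**What to change.** In Section 9.4.1, prespecify an adjusted version of Model 3:

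- For confounding between households, add race/ethnicity, household income (or SNAP/SSI receipt) and essential-worker status. Income and essential-worker status come from the survey that only the head of household completes (5.5), so they cannot explain differences within a family.
- For differences within households, add age group (adult/child) and sex.
- The two randomised factors may be added for precision. They are not needed to control confounding.

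Report the adjusted coefficient as the H3r result wherever it is interpreted as an effect of a positive test. Put the unadjusted coefficient beside it, labelled as the descriptive association.

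The cost is plan wording and a few extra parameters, against about 216 expected positives. No new data are needed: the survey items are already named in Section 9.4.1, sex and race/ethnicity are available under Section 9.4.6, and age group is known from the consent and assent forms (10.1.1.1). Fixing the list in advance also prevents a later choice of covariates. Residual confounding will remain, and the report should say so.
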